9.2	AUDITING AND INSPECTING.....	14
10	ETHICAL CONSIDERATIONS	14
10.1	RISKS	14
10.2	BENEFITS	14
10.3	RISK BENEFIT ASSESSMENT.....	14
10.4	INFORMED CONSENT PROCESS / HIPAA AUTHORIZATION	15
11	STUDY FINANCES	15
11.1	FUNDING SOURCE.....	15
11.2	CONFLICT OF INTEREST	15
11.3	SUBJECT STIPENDS OR PAYMENTS	15
12	PUBLICATION PLAN	15
13	REFERENCES	15
14	ATTACHMENTS	16
15	APPENDICES	16
15.8	SOURCE DOCUMENTS	16
15.9	CASE REPORT FORMS (CRFs).....	17

CONFIDENTIAL

This material is the property of the University of Pennsylvania.

Study Summary

Title	Prospective Use of Awake Endoscopy to Direct Inspire Therapy for Obstructive Sleep Apnea
Short Title	Awake Endoscopy for Inspire
IRB Protocol Number	828956
Methodology	Validation cohort study
Study Duration	2 years
Study Center(s)	Single-center (University of Pennsylvania)
Objectives	
Primary:
 
• To determine the usefulness of awake endoscopy during activation of Inspire device 
Secondary:
 
• To determine optimal configuration of the Inspire upper airway stimulator by quantifying changes in upper airway size for multiple implant configurations• To correlate changes in airway size on endoscopy with sleep study outcomes
Number of Subjects	30-40
Main Inclusion Criteria	
• Patients with moderate to severe OSA• Recipient of Inspire Upper Airway Stimulation Implant surgery• Age 18 or above
Intervention	Awake endoscopic exam will be performed to measure airway size in the retropalatal and retroglossal upper airway regions using different Inspire implant configurations and voltages. The optimal test configuration determined on endoscopy will be tested during a sleep study and compared to the standard-of-care device configuration, with improvements in sleep study outcomes indicating that awake endoscopy is useful during Inspire implant activation.
Statistical Methodology	Paired t-tests will be used to compare differences in AHI and ODI using the test Inspire device configuration/voltage with the standard device configuration/voltage. Paired t-tests will also be used to analyze whether significant differences in airway size exist using different device configurations and voltages. A Pearson correlation test will be used to determine whether changes in airway size correlate with changes AHI and changes in ODI.
Data and Safety Monitoring Plan	PI will be responsible for monitoring the data quality and the ongoing safety of subjects.

CONFIDENTIAL

Background and Study Rationale

1 Introduction

The Inspire Upper Airway Stimulation (UAS) system is an FDA-approved, commercially available, innovative surgical solution for patients with moderate-to-severe obstructive sleep apnea (OSA) that have failed continuous positive airway pressure (CPAP) therapy. It is a surgically-implanted device that is implanted in anesthetized patients using three incisions: a sensing lead that senses inspiration is placed in the lateral intercostal muscles in the low lateral chest, a pacemaker device is placed in the upper chest wall, and a stimulation lead is placed around the hypoglossal nerve in the neck for stimulation of tongue movement. This system is designed to push the tongue forward during inspiration to keep the upper airway open in patients who have tissue collapse causing obstructive sleep apnea. The Inspire device was FDA-approved for the treatment of moderate-to-severe OSA in 2014 and has been implanted in over 1,000 patients to date. Patients undergo outpatient surgery under general anesthesia for implantation then return to see their surgeon at 1 month postoperatively for device activation, which is performed in the awake patient. Current standard-of-care is to activate patients' devices using the "standard configuration" which is the +-+ electrode configuration. This "standard configuration" was determined by the Inspire Corporation, though there are many other possible configurations of the 3-electrode stimulation lead. These different configurations (e.g., +0+, +-+, etc) result in different stimulatory patterns of the hypoglossal nerve and different changes in upper airway architecture, however it is unknown how these changes differ among patients. In the current standard-of-care algorithm, after device activation, patients proceed to outpatient sleep study to titrate their device and assess their response to therapy. While most patients achieve therapeutic benefit from this initial standard setting, a subset of patients for which this is initial configuration is unsuccessful later undergoes awake endoscopy where the surgeon may examine the airway during stimulation with multiple other implant settings. Based on this exam, the surgeon then selects another setting to be tested during a repeat sleep study. **This subset of patients experiences a delay in delivery of effective therapy for OSA. Furthermore, it is unknown whether the patients who are successfully treated with the initial device setting are being optimally treated.** It is possible that these successfully treated patients could have an even greater response with reduction in OSA symptoms and burden of disease if they were to use a different implant setting. The goal of this study is to evaluate the efficacy of awake endoscopy during implant activation. We hypothesize that awake endoscopy can be used during the initial postoperative visit to identify an "optimal" implant configuration based on greatest change in airway size, and that changes in airway size will correlate with an improvement in measures of obstructive sleep apnea on polysomnography.

1.1 Background and Relevant Literature

OSA is characterized by recurrent upper airway obstruction during sleep, resulting in oxygen desaturations, arousals, and sleep fragmentation. OSA affects a significant number of adults in the United States and results in excessive daytime sleepiness and reduced quality of life.¹ OSA is associated with the development of cardiovascular disease including hypertension and stroke, insulin resistance, obesity, cognitive dysfunction, and even death.²⁻⁸ Continuous positive airway pressure (CPAP) is recommended for initial therapy for OSA, however its efficacy is limited by poor compliance in many patients. The Inspire system was developed to treat moderate-to-severe OSA ($20 \leq AHI \leq 65$) in adult patients who are not effectively treated by CPAP. Inspire therapy has been shown to be safe and efficacious, resulting in significantly decreased AHI and ODI as well as decreased symptom burden and improved quality of life.⁹

At present, one month after device implantation, patients are seen in follow up by the primary surgeon. A remote is used to activate the device in the awake patient using a standard configuration (+-+). The stimulator is then titrated to a comfortable voltage level. The patient uses their device at home for one month before undergoing a sleep study, when the voltage is titrated to achieve maximal reduction in

CONFIDENTIAL

apnea-hypopnea index (AHI) while maintaining comfort. If a therapeutic AHI reduction is not achieved during the first post-operative sleep study, patients return to see the surgeon and undergo awake endoscopy in an attempt to determine an optimal configuration. The process of testing multiple different configurations during this visit is not standardized. Patients then undergo one or more additional sleep studies in an attempt to assess therapeutic benefit.

Measurements of airway size have been used to quantify changes in the airway during drug-induced sleep endoscopy, which is a procedure used to visualize the airway during drug-induced sleep to aid in the diagnosis and management for sleep apnea.¹⁰ We hypothesize that airway measurements taken during awake endoscopy can be used to analyze changes in airway size with the Inspire UAS implant, and that this analysis will help guide Inspire therapy, potentially resulting in more efficient and effective therapy delivery.

2 Study Objectives

The aim of this study is to examine a new method of device configuration for the Inspire upper airway stimulator. First, we will attempt to determine optimal configuration by quantifying changes in upper airway size with different implant configurations using awake nasal endoscopy. The configuration/voltage that results in the greatest increase in upper airway size and is tolerated by the patient will be selected. Patients will then undergo a sleep study so that increased airway size may be correlated with changes in sleep study parameters including AHI and oxygen desaturation index (ODI). Airway size and sleep study parameters using the standard device configuration (++)/voltage will be compared to airway size and sleep study parameters using the test, or “optimal,” configuration/voltage to determine the usefulness of awake endoscopy in activation of the Inspire device.

2.1 Primary Objective

- To determine the usefulness of awake endoscopy during activation of Inspire device

2.2 Secondary Objectives (if applicable)

- To determine optimal configuration/voltage of the Inspire upper airway stimulator by quantifying changes in upper airway size with multiple implant configurations
- To correlate change in airway size seen on awake endoscopy with outcomes of observed sleep study including AHI and ODI

3 Investigational Plan

Patients who are undergoing Inspire implantation by the principal investigator will be screened to determine whether they meet inclusion criteria and invited to participate in the study. All components of the study will be performed during visits that are scheduled as part of routine postoperative care; these visits will be modified to incorporate study activities. Written consent will be obtained at Visit 1. Subjects will present to clinic (Visit 1) for awake endoscopy during their regularly scheduled postoperative activation appointment. An aerosolized mixture of xylocaine and oxymetolazone (afrin) will be used as a numbing agent prior to awake endoscopy; this is routinely used for awake endoscopic exams in the ENT clinic. The surgeon will perform awake nasal endoscopy while a clinical assistant or nurse activates and configures the device using the Inspire remote control. Device voltage will be titrated to achieve tongue protrusion across the teeth, which is part of the standard method of activation. Endoscopic exam will be recorded and include visualization of baseline airway with device turned off and airway with multiple test configurations and voltages. At the end of this visit, devices will be set to the standard device configuration that is currently used in routine clinical practice (++) . Patients then routinely use their device at home for the following month. The recorded exam will be used by a single blinded member of

CONFIDENTIAL

the study team to formally measure and analyze airway size in the various conditions after this visit and the “optimal” test configuration will be determined based on airway measurements. Subjects subsequently will undergo an in-lab sleep study for titration of their device (Visit 2). Titration sleep study will ensue with the Inspire device in A) the standard (+++) configuration and B) the “optimal” test configuration. Voltage used with each implant configuration may be increased to achieve effective reduction in AHI at the discretion of the sleep physician; this is routinely performed during titration polysomnography in our current clinical practice. At the end of the sleep study, the device will be returned to the standard setting until further follow up with their sleep medicine physician. This concludes the subject’s participation in the study. Subjects will obtain the results of the sleep study and discuss further device management with their sleep medicine physician during routine follow up.

3.1 General Design

This is a cohort study that will evaluate the use of awake endoscopy as a diagnostic tool used to determine optimal configuration of the Inspire UAS device.

3.2 Allocation to Interventional Group

All patients will receive the same intervention.

3.3 Study Measures

Awake endoscopy will be performed during Visit 1 during which airway size will be video recorded at rest with implant off and with a standardized sequence of implant configurations that were determined by Inspire Corporation during pre-market testing including +++, ---, o-o, -o-, and -+-+. These settings will be tested to determine the voltage at which patients sense tongue movement (sensation threshold) and the voltage at which the tongue is visualized protruding from rest past the teeth (functional threshold). The different electrode configurations will then be tested at various voltages above the subject’s measured functional thresholds.

Measurements of cross-sectional, anterior-to-posterior, and lateral airway size in the retropalatal and retroglossal regions will be taken from recorded endoscopic exams using the image analysis program Amira by Visage Imaging (Richmond, Victoria, Australia). Measurements will take place between Visits 1 and 2. Standard AHI and ODI measurements will take place during in-lab sleep study (Visit 2). Efficacy of awake endoscopy to determine optimal device configuration will be assessed by comparing cross-sectional airway size (retropalatal and retroglossal), AHI and ODI with the standard device configuration compared to airway size, AHI and ODI with the test configuration. In patients for whom the standard configuration (+++) results in greatest airway size, this will be the sole configuration tested during sleep study, and identical values for airway size, AHI, and ODI will be used in analysis comparing the standard configuration with the “test” configuration.

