5.2 Study Intervention

5.2.1 Visit 1: Otolaryngology Clinic for Awake Endoscopy

- Informed consent
- Vital signs: HR, RR, BP, SpO₂, BMI
- Targeted Head and Neck Physical Exam
 - Tongue size, lateral peritonsilar narrowing, palate shape, Modified Mallampati score
- Recorded exam of awake endoscopy at rest and with standardized configurations detailed in section 3.3 (Attachment 1)
 - Measurement and analysis of airway size to be completed by single co-investigator between Visits 1 and 2. Configuration resulting in greatest airway size will be used as test configuration during Visit 2 sleep study.

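### Visit 1 uses one standardized sequence of configurations with no order control, so any drift during the exam would be confounded with configuration

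*Combined protocol and SAP*

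**What the plan says.** Section 3 (Investigational Plan) has the topical agent given first: "An aerosolized mixture of xylocaine and oxymetolazone (afrin) will be used as a numbing agent prior to awake endoscopy". No waiting time before the first recording is stated. The same section covers the reference: "Endoscopic exam will be recorded and include visualization of baseline airway with device turned off". No second device-off recording is described.

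Section 3.3 then runs the configurations "with a standardized sequence of implant configurations that were determined by Inspire Corporation during pre-market testing", and lists them as "including +++, ---, o-o, -o-, and" one more. The configuration that 3.3 calls standard is printed first. After thresholds are found there is a further pass: "The different electrode configurations will then be tested at various voltages above" the functional threshold. The order of that pass is not given.

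Section 5.2.1 refers back to 3.3 ("Recorded exam of awake endoscopy at rest and with standardized configurations detailed in section 3.3") and sets the selection rule: "Configuration resulting in greatest airway size will be used as test configuration during Visit 2 sleep study". Section 3.2 adds: "All patients will receive the same intervention".

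Section 6.3 is introduced as covering randomization and blinding. It lists two measures: recruiting every eligible subject, and measuring airway size without knowledge of subject history. Neither concerns the order of configurations.

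**The concern.** Several things could change while the scope is in place: time since the spray, tolerance of the scope and of stimulation, and tongue fatigue. If every subject meets the configurations in the same order, any systematic change over the exam falls on the same configurations each time. Enrolling more subjects does not average it out, and no analysis of the recordings can separate the two afterwards.

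Three results use these recordings:

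- **The choice of test setting.** A rule that takes the largest of several readings responds to small systematic shifts.
- **How often the standard wins.** Under 3.3, when the standard has the largest airway it is the only configuration studied at Visit 2, and identical values enter the comparison. The win rate therefore sets how many zero differences enter the paired t-test.
- **The airway-size results.** These are the secondary endpoint in 3.4.2 and the airway t-test in 6.2.

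**Working it through.** **The plan's own figures.** The plan gives no figure for drift or for reading error. Its one calculation is the sample size in 6.1. For a paired test with effect size 0.5, two-sided alpha 0.05 and power 80%, n = ((1.960 + 0.842)/0.5)² = 31.4, so 32, close to the stated figure of about 30 (an exact t calculation needs 34). Order control does not change this number.

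**Model for the illustration.** From the documents: five listed configurations, and selection of the largest. Everything else is assumed: the standard is run first, there is one reading per configuration, log airway size has independent noise, and a linear drift of log(1 + g) runs from first to last position. Each case was simulated with at least 100,000 subjects.

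| Assumed settings | Drift g | Standard (first) chosen | Last chosen |
|---|---|---|---|
| Truly equal, noise SD 0.10 | 0 | 20% | 20% |
| | +5% | 13.5% | 27% |
| | +10% | about 9% | 35% |
| | +20% | 3% | 48% |
| | −10% | 37% | 8% |
| Truly equal, noise SD 0.20 | +10% | 13.5% | 27% |
| | +20% | 9% | 34% |
| Truly different (SD 0.20), noise SD 0.10 | +10% | about 14% | 26–27% |
| | +20% | 10% | 33% |

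The size of the shift follows from log(1.10) = 0.095. That is about one noise SD when the noise SD is 0.10, and a smaller fraction when the settings truly differ.

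For 30 subjects, standard wins (and so zero differences) would number 30 × 0.20 = 6 without drift. At +10% drift they would be 30 × 0.09 ≈ 3 with equal settings, or 30 × 0.14 ≈ 4 with truly different ones.

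**Effect on the airway comparison** (equal settings, noise SD 0.10). The mean apparent log-size gain of the chosen setting over the standard is 0.116 with no drift, purely from picking the maximum. In a fixed order it is 0.172 at +10% and 0.073 at −10%. With the order varied between subjects it is 0.124 at +10%. The distortion falls from 0.172 − 0.116 = 0.056 to 0.124 − 0.116 = 0.008, and each setting is again chosen in 20% of subjects.

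**Effect on the AHI and ODI comparison.** These outcomes are measured at Visit 2, so Visit 1 drift acts on them only through a less accurate choice. A second simulation treated all setting-to-setting variation as real and expressed drift in SDs of that variation. The drift-free airway gain of the chosen setting was 1.16 SD with no drift, 1.14 at ±0.5 SD and 1.08 at ±1 SD. The losses are 0.02/1.16 ≈ 2% and 0.08/1.16 ≈ 7%. Randomising the order gave the same 1.14 and 1.08: it spreads the error evenly over configurations but does not remove it from an individual subject's choice.

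**The case against.** The strongest reply is that this is a risk and not a demonstrated bias. No section reports drift, fatigue, or any effect of the spray on retropalatal or retroglossal size. With zero drift there is no problem. That stands, and the point is conditional for this reason.

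A reader might also infer that the standard is always recorded first and each configuration always sits at one fixed time. The documents do not support that. The list in 3.3 is introduced by a word meaning that it need not be complete, and it is not called the running order. Sequence may mean no more than a fixed set. Each configuration appears in at least two passes and at several voltages, and the order of the second pass is not stated. The 30 minutes in the appendix covers the whole of Visit 1, including consent and examination, so the exam itself is shorter. What remains is that a fixed order ties each configuration to its position wherever the standard falls, and that an unstated order is uncontrolled and not said to be recorded.

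Standardization is also deliberate. Section 1.1 criticises present practice for lacking it, and 6.1 calls the study a pilot. A pre-prepared balanced list is still a standardized procedure, so this argues for writing the order down and not against varying it.

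Finally, varying the order does not improve the choice for any one subject. That is correct. The benefit is to the airway-size comparison and to which configurations are favoured across the cohort.

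**Conclusion.** The point holds as a conditional one. The plan describes one standardized sequence, a pick-the-largest rule, and neither order control nor a repeat reference. Order effects, if present, would be confounded with configuration in the choice of setting, the standard's win rate and the Visit 1 airway comparison.

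The size is unknown. With 10% noise, the standard assumed first and an assumed +10% drift, the standard's win rate falls from 20% to about 9% if the settings are truly equal, and to about 14% if they truly differ with SD 0.20. The second case is closer to the study's premise that configurations act differently. Downward drift moves the rate the other way.

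A reader might go further and infer that the primary result would be biased in favour of endoscopy. The documents do not support that: AHI and ODI come from a later visit, so a poorer choice at Visit 1 can dilute a real benefit but cannot manufacture one. In the illustration the dilution is about 2% to 7% of the airway gain. How that carries over to AHI depends on a correlation the study has yet to estimate. This is a worthwhile, low-cost improvement and not a flaw that undermines the primary comparison.

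**What to change.** Keep the same configurations and amend 3.3 and 6.3 as follows.

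1. State which recordings are used for measurement and the order in which they are made.
2. Assign the order of the above-threshold recordings from a pre-prepared balanced list. A balanced Latin square is preferable to simple cyclic rotations, which keep most neighbouring pairs and so leave carry-over in place. For five configurations, balance for neighbours takes two squares, or 2 × 5 = 10 orders, which is 3 to 4 subjects per order at 30 to 40 subjects.
3. Repeat the device-off and standard recordings once at the end. Both are useful because drift at rest and drift under stimulation may differ.
4. Record order and time since spray on the CRF, and include position in the airway-size analysis.

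The repeats serve mainly to estimate average drift. With 10% noise, one subject's start-to-end difference has SD √2 × 0.10 = 0.14 in log size, larger than a 10% drift (0.095). Over 30 subjects the standard error is 0.14/√30 = 0.026, before any variation in drift between subjects. The plan should therefore say in advance whether the choice of test setting uses unadjusted readings.

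The cost is a printed list, two short extra recordings, two CRF fields and a few sentences of protocol text. There is no added visit and no change in sample size. The drawbacks are that the assistant follows a different order for each subject and the exam is slightly longer.

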3.4 Study Endpoints

3.4.1 Primary Study Endpoint

The primary endpoint is to assess the efficacy of awake endoscopy in determining optimal implant configuration during implant activation. A decrease in AHI and ODI with test configuration compared to standard configuration will indicate that awake endoscopy is useful for identifying optimal implant configuration compared to the current method of activation without endoscopy.

CONFIDENTIAL

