5.2.2 Visit 2: In-lab Sleep Study

- Polysomnography
 - Half of study using standard implant configuration, half of study using test configuration determined by awake endoscopy.

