5.5 Efficacy Evaluations

Efficacy of the intervention being tested (awake endoscopy to determine optimal Inspire device configuration) will be assessed by comparing AHI and ODI using the standard device configuration compared to AHI and ODI with the test configuration. The intervention will be deemed efficacious if a statistically significant reduction in AHI and/or ODI is achieved with the test configuration determined using awake endoscopy compared to the standard device setting.

CONFIDENTIAL

6 Statistical Plan

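### A lower AHI/ODI shows that the endoscopy-selected setting beats the standard one; it does not show, as 3.4.1 and 5.5 conclude, that endoscopy identified the optimal setting

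*Combined protocol and SAP*

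**What the plan says.** The primary objective (2.1) is the usefulness of awake endoscopy at activation. Under 3.3 the airway is recorded "with a standardized sequence of implant configurations that were determined by Inspire Corporation during pre-market testing including" five listed patterns, one of them the standard. Section 5.2.1 makes the configuration with the largest airway the test setting.

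At the sleep study (5.2.2) the night is divided: "Half of study using standard implant configuration, half of study using test configuration determined by awake endoscopy". Section 3.2 adds that "All patients will receive the same intervention", so there is no control group. If the standard setting gives the largest airway, it alone is tested, and 3.3 enters identical values for both conditions.

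From this one contrast, 3.4.1 concludes that a decrease "will indicate that awake endoscopy is useful for identifying optimal implant configuration compared to the current method of activation without endoscopy". Section 5.5, which defines the intervention as endoscopy used to find the best configuration, states: "The intervention will be deemed efficacious if a statistically significant reduction in AHI and/or ODI is achieved with the test configuration". The Study Summary also reads better sleep-study outcomes as showing that endoscopy is useful.

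The analysis in 6.2 is a paired t-test of test against standard. A secondary Pearson correlation relates airway change to AHI and ODI change. It is not part of the success rule.

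**The concern.** Three questions are folded into one test: whether the selected setting beats the default, whether it is the best candidate, and whether endoscopy is the reason for the gain. The data answer only the first.

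If the alternatives are better than the default on average, any rule that moves patients off the default will lower AHI, including a random pick. The plan would then declare endoscopy efficacious. A reader could take the result as support for endoscopy in every patient at activation when the data show only that the default is weak.

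**Working it through.** **1. What is observed.**

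| Question | Data needed | In the plan? |
|---|---|---|
| Does the selected setting beat the standard? | AHI/ODI on both | Yes (5.2.2) |
| Is it the best candidate? | AHI/ODI on unselected candidates | No |
| Is the gain due to endoscopic selection or to leaving the default? | AHI/ODI on a non-standard setting chosen without endoscopy, or knowledge that the default is no worse on average | No; only indirect evidence from the 6.2 correlation |

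**2. The plan's own figure.** Section 6.1 gives about 30 subjects for a 50% effect size, alpha 0.05 and beta 0.2. Reading this as a standardised paired difference d = 0.5, two-sided: n = ((1.960 + 0.842)/0.5)² = 31.4, so 32, which agrees with about 30. The exact t calculation gives 34, and power at 30 is 75.4%.

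**3. A pick with no information.** All effect sizes and SDs here are assumed. Each of five configurations is equally likely to be picked. An alternative minus the standard has mean −δ and between-patient SD 5 events/h. Measurement adds SD 9 to the paired difference. A standard pick is entered as zero, as in 3.3. Then:

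- size of mean reduction = 0.8δ
- variance = 0.8(5² + 9² + δ²) − (0.8δ)²

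For δ = 5 the mean is 4.0 and the variance is 0.8 × 131 − 16 = 88.8. The SD is 9.42 and d = 4.0/9.42 = 0.42. At n = 30 the noncentrality is 0.42 × √30 = 2.3, which gives power of about 61%. Simulation of the AHI test, counting two-sided 0.05 results in the favourable direction, gives:

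| Mean advantage δ (events/h) | n = 30 | n = 40 |
|---|---|---|
| 0 | 2% | 3% |
| 3 | 27% | 35% |
| 5 | 62% | 75% |
| 8 | 95% | 99% |

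In every row the truly best setting is picked 1 time in 5. The plan's d = 0.5 is reached when 0.64δ² = 0.25(84.8 + 0.16δ²), that is δ² = 21.2/0.60 = 35.3 and δ = 5.9. In this model, an average advantage of about 6 events/h gives the design effect with nothing contributed by endoscopy.

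**4. Good selection against a weak default.** A second model lets the standard setting vary between patients too (SD 5) and uses noise SD 5 per half-night. At n = 30, an uninformative pick with δ = 5 succeeds in 65% of trials and finds the best setting 20% of the time. An informative pick (correlation 0.6 between airway and benefit) with δ = 0 succeeds in 58% and finds the best setting 47% of the time. The success rates are close although the explanations are opposite.

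**5. The planned correlation.** Subjects who stay on the standard enter as zero airway change and zero AHI change. If switched subjects gain on both measures on average, these points create a correlation even when the size of the airway gain is uninformative. Take the model of step 3 with an assumed airway gain of mean 30 and SD 15, unrelated to AHI gain. At n = 30 a favourable significant correlation then appears in about 9–11% of trials at δ = 5 and 22% at δ = 8. Restricted to switched subjects it appears in about 3%.

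The restricted correlation has low power. With informative endoscopy (correlation 0.6, noise SD 9) it is significant in about 17–23% of trials at n = 30–40. A rerun in which the standard setting also varies gave 23% and 30%.

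**The case against.** The comparator is the one the plan names. Activation today uses the default without endoscopy. Endoscopy comes later, and only for some: "If a therapeutic AHI reduction is not achieved during the first post-operative sleep study, patients return to see the surgeon and undergo awake endoscopy". Endoscopy-guided setting against default in the same patient is a legitimate pragmatic contrast, and earlier access to effective therapy is a stated aim (sections 1 and 10.2). This stands. A reader might infer that the comparison with current activation is itself invalid and should go; the documents do not support that.

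A reader might also infer that the alternatives really do beat the default. Nothing in the documents says so, and section 1 says most patients benefit on the standard setting. Nor do the documents say that the default is as good on average, which the attribution to endoscopy would require.

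Section 2 defines the selection operationally, as the largest tolerated airway increase. The airway-to-outcome link is a planned secondary analysis, and 6.1 calls the study a pilot. This softens the point, but 3.4.1 and 5.5 still draw the full conclusion from the primary contrast alone.

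Finally, one might want usefulness claimed only if the correlation is significant. At the power in step 5, that rule would usually withhold the claim when endoscopy works.

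**Conclusion.** The conclusions in 3.4.1 and 5.5 are wrong as written. The design supports the statement that the endoscopy-selected setting gives lower AHI/ODI than the standard setting used at activation. It does not support optimality, and it cannot tell good selection from a weak default. This follows from which settings are tested in sleep and needs no simulation.

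The percentages are illustrative. They rest on assumed effect sizes and SDs and on AHI alone, whereas 3.4.1 asks for both measures and 5.5 for either. Even the narrower statement assumes that half-night order, which is not stated, and discretionary voltage increases do not bias the contrast. The trial remains informative; what must change is the claim.

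**What to change.** 1. In 3.4.1, 5.5 and the Study Summary, state the conclusion as: *the endoscopy-selected setting gives lower AHI/ODI than the standard setting used at activation without endoscopy*. Drop the claim of identifying the optimal configuration. Keep the comparison with standard activation.
2. Add a descriptive table of how often each configuration was selected, with the mean AHI and ODI difference for each. With 30–40 subjects over five patterns the rows will be small, so attach no decision rule.
3. In 6.2, report the correlation also among subjects whose setting changed, beside the all-subject version.
4. Say that items 2 and 3 are supporting evidence on whether endoscopic selection, rather than leaving the default, explains any gain. Do not make the claim conditional on a significant correlation.

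Cost: text changes, one table and one additional correlation analysis, with no extra patients or procedures. The downside is a narrower headline claim.
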